### **6.11. Health Outcomes/Quality-of-Life Analyses**

The health outcomes and quality-of-life (QOL) measures are ASAS HI, SF-36, Fatigue NRS, JSEQ, WPAI-SpA, and QIDS-SR16.

The analyses of health outcomes and QOL measures for Period 2 will be based on the ITT Population.

Table RHBX.6.6 includes the description and derivation of the health outcomes and QOL measures.

Table RHBX.6.7 provides the detailed analyses including analysis type, method and imputation, population, time point, and treatment group comparisons for health outcomes and QOL analyses.

**Table RHBX.6.6. Description and Derivation of Health Outcomes and Quality-of-Life Measures**

Measure	Description	Variable	Derivation / Comment	Imputation Approach if with Missing Components
ASAS Health Index	The ASAS-Health Index (ASAS HI) is a disease specific health-index instrument designed to assess the impact of interventions for SpA, including axSpA. The 17 item instrument has scores ranging from 0 (good Health) to 17 (poor Health) (Kiltz et al. 2013). Each item consists of 1 question that the patient needs to respond to with either “I agree” (score 1) or “I do not agree (score 0).” A score of “1” is given where the item is affirmed, indicating adverse health.	ASAS HI	All item scores are summed to give a total score or index. Range: 0 to 17 0 (good health) and 17 (poor health) Note, items # 7 and #8 may not be applicable for some patients. For those patients who ticked the response “not applicable”, the sum score is analyzed based on n=16 or n=15, respectively.	If $\geq 4$ items ( $>20\%$ ) have missing response, then ASAS HI is missing. If $<4$ items ( $\leq 20\%$ ) missing, then imputed sum = sum of scores from nonmissing items $\times n / (n - \text{no. of missing items})$ , where n is the total number of applicable items, e.g. 15, 16, or 17. [ASAS (WWW)].
		ASAS HI change from baseline	Calculated as: observed ASAS HI – baseline ASAS HI	Missing if baseline or observed value is missing
		Proportion of patients with $\geq 3$ improvement from baseline	The smallest detected change of ASAS HI is 3.	Missing if baseline or observed value is missing
		Proportion of patients reaching Good ASAS HI (defined as ASAS HI $\leq 5$ )		Missing if baseline or observed value is missing
Medical Outcomes Study 36-item Short-Form Health Survey	The SF-36 is a 36-item patient-administered measure designed to be a short, multipurpose assessment of health in the areas of physical functioning, role–physical, role–emotional, bodily pain, vitality, social functioning, mental health, and general health. The 2 overarching domains of mental well-being and physical well-being are captured by the Mental Component Summary and Physical Component Summary scores. The	8 associated domain scores: 
 
• Physical Functioning,
 
• Role Physical,
 
• Bodily Pain,
 
• General Health,
 
• Vitality,
 
• Social Functioning,
 
• Role Emotional,
 
• Mental Health
 
	Per copyright owner, the QualityMetric Health Outcomes™ Scoring Software 4.5 will be used to derive SF-36 domain and component scores. After data quality-controls, the SF-36 software will re-calibrate the item-level responses for calculation of the domain and component scores. These raw scores will be transformed into the domain scores (t-scores) using the 1-week recall period. The procedure to derive the SF-36 scores is described in Appendix 6 . It	All collected data will be imported into SF-36 software and “Maximum Data Recovery” will be selected for “Missing Score Estimator”

Measure	Description	Variable	Derivation / Comment	Imputation Approach if with Missing Components
	summary scores range from 0 to 100; higher scores indicate better levels of function and/or better health. Items are answered on Likert scales of varying lengths. The SF-36 version 2 (acute version) will be used, which utilizes a 1-week recall period (Ware 2000)).	2 component Scores: 
 
• MCS Score
 
• PCS Score
 
	entails exporting the patient data in a CSV or tab-delimited file for import, generation of the SF-36 scores and reports, and export of the calculated scores in a CSV or tab-delimited file for integration into SDTM/ADaM datasets.	
		PCS, MCS and domain scores (for both transformed and norm-based scores) change from baseline – major secondary for PCS	Calculated as: observed score – baseline score	Missing if baseline or observed value is missing
Fatigue Severity Numeric Rating Scale	The fatigue severity NRS is a patient-administered single-item 11-point horizontal scale anchored at 0 and 10, with 0 representing “no fatigue” and 10 representing “as bad as you can imagine” (Naegeli et al. 2013). Patients rate their fatigue (feeling tired or worn out) by circling the 1 number that describes their worst level of fatigue during the previous 24 hours.	Fatigue Severity NRS	Range: 0 to 10. 0 (no fatigue) and 10 (as bad as you can imagine).	Single item, missing if missing
		Fatigue Severity change from baseline	Calculated as: observed Fatigue Severity NRS – baseline Fatigue Severity NRS	Missing if baseline or observed value is missing
Work Productivity and Activity Impairment Questionnaire– Spondyloarthritis	The Work Productivity Activity Impairment—Spondyloarthritis (WPAI-SpA) consists of 6 questions to determine employment status, hours missed from work because of spondyloarthritis, hours missed from work for other reasons, hours actually worked, the degree to which spondyloarthritis affected work productivity while at work, and the	percentage of absenteeism	% work time missed due to problem: $(Q2/(Q2 + Q4))*100$	if Q2 or Q4 is missing, then missing
		percentage of absenteeism - change from baseline	Calculated as: observed value – baseline value	if baseline or observed value is missing, then missing
		percentage of presenteeism	% impairment while working due to problem: $(Q5/10)*100$	if Q5 is missing, then missing
		percentage of presenteeism -	Calculated as: observed value – baseline value	if baseline or observed value is missing, then missing

Measure	Description	Variable	Derivation / Comment	Imputation Approach if with Missing Components
	
degree to which spondyloarthritis affected activities outside of work. The WPAI-SpA has been validated in the rad-axSpA patient population (Reilly et al. 2010). Four scores are derived: percentage of absenteeism, percentage of presenteeism (reduced productivity while at work), an overall work impairment score that combines absenteeism and presenteeism, and percentage of impairment in activities performed outside of work. Greater scores indicate greater impairment (Reilly Associates Health Outcomes Research [WWW]).
	change from baseline		
		overall work impairment score	$\% \text{ overall work impairment due to problem: } (Q2/(Q2+ Q4) + [(1-Q2/(Q2+Q4))*(Q5/10)])*100$	if any of Q2, Q4, or Q5 is missing, then missing
		overall work impairment score - change from baseline	Calculated as: observed value – baseline value	if baseline or observed value is missing, then missing
		percentage of activity impairment	$\% \text{ activity impairment due to problem: } (Q6/10)*100$	if Q6 is missing, then missing
		percentage of activity impairment - change from baseline	Change from baseline is calculated as: observed value – baseline value	if baseline or observed value is missing, then missing
Jenkins Sleep Questionnaire	
The Jenkins Sleep Evaluation Questionnaire (JSEQ) is a 4 item scale designed to estimate sleep problems in clinical research. The JSEQ assesses the frequency of sleep disturbance in 4 categories: 1) trouble falling asleep, 2) waking up several times during the night, 3) having trouble staying asleep (including waking up far too early), and 4) waking up after the usual amount of sleep feeling tired and worn out. Patients report the numbers of days they experience each of these problems in the past month on a 6 point Likert Scale ranging from 0 = “no days” to 5 = “22-30 days.”
	JSEQ score	
Sum of 4-item score (each on a 6-point Likert scale, 0 = no days and 5 = 22-30 days). Range: 0 to 20, higher scores indicating greater sleep disturbance (Deodhar et al. 2010)
	Missing if >20% items (ie, any of the 4) are missing
		JSEQ score change from baseline	Change from baseline calculated as: observed JSEQ – baseline JSEQ	Missing if baseline or observed value is missing
Quick Inventory of Depressive	See Section 6.13.6 for description of QIDS-SR16	9 Domains	See Section 6.13.6 for description of each domain	See Section 6.13.6

Measure	Description	Variable	Derivation / Comment	Imputation Approach if with Missing Components
Symptomatology-self report 16 items		Change from baseline in each domain	Calculated as: observed domain score – baseline domain score	Missing if baseline or observed value is missing
		Item 12 Thought of Death or Suicide	Range: 0 to 3.	Missing if the item is missing.
		Change from baseline in Item 12 Thought of Death or Suicide	Calculated as: observed item score – baseline individual item score	Missing if baseline or item is missing
		QIDS-SR16 total score	See Section 6.13.6 for description of QIDS-SR16 total score	See Section 6.13.6
		Change from baseline in QIDS-SR16 total score	Calculated as: observed total score – baseline total score	Missing if baseline or observed value is missing
		Proportion of patients with at least a 50% decrease in QIDS-SR16 total score	% reduction from baseline calculated as: $100 \times \frac{Baseline - Observed\ score}{Baseline}$ If the value of % reduction from baseline is $\geq 50$ , patients had at least a 50% decrease in QIDS-SR16 total score.	Missing if baseline or observed score is missing

Abbreviations: ADaM = Analysis Data Model; ASAS = Assessment of Spondyloarthritis International Society; axSpA = axial spondyloarthritis; CSV = comma-separated values; MCS = mental component summary; NRS = numeric rating scale; PCS = physical component summary; SDTM = Study Data Tabulation Model; SF-36 = Medical Outcomes Study 36-Item Short-Form Health Survey; SpA = spondyloarthritis.

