#### **8.1.2.18. Work Productivity and Activity Impairment Questionnaire— Spondyloarthritis**

The WPAI-SpA consists of 6 questions to determine employment status, hours missed from work because of spondyloarthritis, hours missed from work for other reasons, hours actually worked, the degree to which spondyloarthritis affected work productivity while at work, and the degree to which spondyloarthritis affected activities outside of work. The WPAI-SpA has been validated in the rad-axSpA patient population (Reilly et al. 2010). Four scores are derived: percentage of absenteeism, percentage of presenteeism (reduced productivity while at work), an overall work impairment score that combines absenteeism and presenteeism, and percentage of impairment in activities performed outside of work. Greater scores indicate greater impairment (Reilly Associates Health Outcomes Research [WWW]).

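### WPAI-SpA overall work impairment is set to missing when Q5 is blank, even for a patient who lost all work hours to the disease, for whom the SAP's own formula gives 100 whatever Q5 is

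*SAP*

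**What the plan says.** The WPAI-SpA rows of SAP Table RHBX.6.6 define four scores. Neither document numbers the six questions in its description, but the order gives the meaning of Q2 to Q4: "hours missed from work because of spondyloarthritis, hours missed from work for other reasons, hours actually worked". Q5 follows and concerns "the degree to which spondyloarthritis affected work productivity while at work" (Protocol 8.1.2.18).

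- Overall work impairment is the disease-related share of hours missed plus the remaining share weighted by Q5. Without its opening bracket, the formula is "Q2/(Q2+ Q4) + [(1-Q2/(Q2+Q4))*(Q5/10)])*100". Its missing rule is "if any of Q2, Q4, or Q5 is missing, then missing", with no exception.
- Absenteeism, 100 × Q2/(Q2+Q4), has the rule "if Q2 or Q4 is missing, then missing".
- Presenteeism, 100 × Q5/10, has the rule "if Q5 is missing, then missing".
- Change from baseline in the overall score has the rule "if baseline or observed value is missing, then missing".

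SAP Table RHBX.6.7 analyses the changes by ANCOVA with mBOCF in the ITT population at Weeks 16 and 52. The Protocol's Schedule of Activities collects the WPAI-SpA at Weeks 0, 16 and 52 and at early termination. SAP 6.3.2 ties the mBOCF carry-forward to stopping study drug or starting ixekizumab rescue.

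**The concern.** A patient who lost every working hour to spondyloarthritis has Q2>0 and Q4=0. That patient has no time at work to rate, so Q5 is the item most likely to be left blank. The rule then returns a missing overall score, although the formula does not need Q5 in this case. The patient with the worst possible outcome can therefore drop out of the overall score and its change from baseline, while the same record counts as 100 for absenteeism. Whether a value is lost then depends on the outcome itself, which is the kind of missingness an ANCOVA on the remaining patients does not correct. Elsewhere the SAP does provide for items that do not apply: Table RHBX.6.6 rescales the ASAS Health Index when items 7 and 8 are not applicable. The WPAI-SpA has no such provision.

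**Working it through.** **1. The formula at zero hours worked.** Let A = Q2/(Q2+Q4). The overall score is 100 × [A + (1−A) × Q5/10].

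- Q2=40, Q4=0: A = 1, so the score is 100 × [1 + 0 × Q5/10] = 100 for every Q5.
- Q2 = 1, 8, 20, 40 and 60 hours were each run with Q4=0 and Q5 from 0 to 10. All 55 combinations give 100.0.
- With Q5 blank, the SAP rule returns missing for each of these Q2 values, while absenteeism is 100 × Q2/(Q2+0) = 100.

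The overall score is never below absenteeism, because (1−A) × Q5/10 cannot be negative. Absenteeism of 100 therefore forces an overall score of 100.

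**2. Where the present rule is right.** If some hours were worked, Q5 matters. For a 40-hour week with the remaining hours missed because of the disease, the score as Q5 runs from 0 to 10 is:

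- Q4=1: 97.5 to 100
- Q4=4: 90 to 100
- Q4=8: 80 to 100
- Q4=20: 50 to 100

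Setting these to missing when Q5 is blank is reasonable. If Q2=Q4=0 (no hours worked and none missed because of the disease), A is 0/0 and the score is undefined, not 100.

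**3. Whether a later step restores the value.** The change-from-baseline rule passes the missing score on. For a patient still on the original treatment, SAP 6.3.2 states no imputation. If an earlier score were carried forward anyway, the known 100 would still go unused.

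**4. Size, under assumptions.** The documents give no frequency of full absence and no WPAI-SpA means. Assume means of 40 (placebo) and 30 (ixekizumab) among the other employed patients, full-absence rates p (placebo) and q (ixekizumab), and Q5 blank in all fully absent patients.

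- Placebo mean with them included: 40(1−p) + 100p = 40 + 60p
- Ixekizumab mean with them included: 30(1−q) + 100q = 30 + 70q
- True difference: −10 − 60p + 70q
- Difference under the rule: 30 − 40 = −10.0 in every case

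| Full absence, placebo v ixekizumab | True difference | Effect of the rule |
|---|---|---|
| 2% v 1% | −10 − 1.2 + 0.7 = −10.5 | understates |
| 4% v 1% | −10 − 2.4 + 0.7 = −11.7 | understates |
| 6% v 2% | −10 − 3.6 + 1.4 = −12.2 | understates |
| 10% v 4% | −10 − 6.0 + 2.8 = −13.2 | understates |
| 4% v 4% | −10 − 2.4 + 2.8 = −9.6 | overstates |
| 10% v 10% | −10 − 6.0 + 7.0 = −9.0 | overstates |

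The sign changes where 60p = 70q, that is at p/q = 70/60, about 1.17.

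Within a single arm, with an assumed mean of 45 among scorable patients, the observed mean is too low by s × (100 − 45) when a share s is lost: 0.55, 1.65, 2.75 or 5.5 points for s = 1%, 3%, 5% or 10%.

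**The case against.** The strongest objection is that nothing in the documents shows that Q5 will be blank. Protocol 10.2.1 has patient questionnaires entered directly on a tablet. Neither document says whether an item can be skipped, and the questionnaire's skip pattern is not shown. If any Q5 value is recorded, the formula already returns 100. This stands. A reader might infer that the rule drops every fully absent patient, but the documents support only the conditional statement.

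A reader might also infer that every value the rule removes is 100. That holds only for Q2>0 with Q4=0. The rule also removes records with Q4>0 and a blank Q5, or with Q2 or Q4 blank, and there the score is undetermined.

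A third tempting reading is that the rule understates the benefit of ixekizumab. The documents do not settle the direction, and the last two rows of the table reverse it. The table also compares visit means, whereas the endpoint is a baseline-adjusted change. Blanks at baseline should balance between arms in expectation, and their effect on the treatment difference was not computed.

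Exposure at Week 52 is narrower than it may look. A patient rescued between Weeks 16 and 44 has an earlier value carried forward, so the Week 52 questionnaire is not used. That also stands, although a Week 16 score already lost to the rule cannot be the value carried. Finally, full absence still shows in absenteeism, and Q6 still gives activity impairment. That limits the consequence but does not make the overall score right.

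**Conclusion.** The rule as written gives a wrong result in one definable case: Q2>0, Q4=0 and Q5 blank. The formula then determines a score of 100, and the SAP discards it. This follows from the SAP's own formula and needs no assumption. How often it happens does rest on an assumption, because the documents give neither the questionnaire's completion rules nor any rate of full absence. The loss is tied to the outcome, but its size and direction are unknown. In the illustrations, the true difference lies between −13.2 and −9.0, against −10.0 under the rule. If Q5 is always answered, the effect is zero. It is confined to one of four WPAI scores, an other secondary endpoint outside the multiplicity scheme, and no primary or major secondary analysis is touched. Severity: minor.

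**What to change.** In SAP Table RHBX.6.6, replace the missing rule for overall work impairment with: *If Q2>0 and Q4=0, overall work impairment = 100 regardless of Q5; otherwise missing if any of Q2, Q4 or Q5 is missing.*

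The condition Q2>0 keeps out the 0/0 case, and the rule for Q4>0 is unchanged, so no other patient's score moves. Scoring 100 here evaluates the formula; it is not an imputation. The cost is one line of SAP text and one programming condition, with no new data. If Q5 turns out never to be blank in these patients, the change has no effect on the results.

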**Table RHBX.6.7. Description of Health Outcomes and Quality-of-Life Analyses**

Measure	Variable	Analysis Method (Sections 6.1 and 6.3)	Population (Section 6.1.1)	Comparison/Time Point	Analysis Type
36 item Short Form Health Survey (SF-36)	PCS (Major Secondary), change from baseline	MMRM	ITT Population	IXE80Q2W & IXE80Q4W vs. placebo at Weeks 16 and 52 and all other postbaseline visits in Period 2	Major secondary efficacy analysis is MMRM analysis for ITT Population comparing IXE80Q2W & IXE80Q4W vs. placebo at Weeks 16 and 52 (Section 6.10.2).
		ANCOVA with mBOCF	ITT Population	IXE80Q2W & IXE80Q4W vs. placebo at Weeks 16 and 52 and all other postbaseline visits in Period 2	Health Outcomes/QOL analyses (Section 6.11).
		Descriptive statistics	IR Population	Period 2 post initiation of biologic rescue of ixekizumab 80 mg Q2W	Health Outcomes/QOL analyses (Section 6.11).
	MCS, domain scores (for both transformed and norm-based scores), change from baseline	MMRM	ITT Population	IXE80Q2W & IXE80Q4W vs. placebo at Weeks 16 and 52 and all other postbaseline visits in Period 2	Health Outcomes/QOL analyses (Section 6.11).
		ANCOVA with mBOCF	ITT Population	IXE80Q2W & IXE80Q4W vs. placebo at Weeks 16 and 52 and all other postbaseline visits in Period 2	Health Outcomes/QOL analyses (Section 6.11).
	ASAS Health Index (ASAS HI)	ASAS HI change from baseline -	MMRM	ITT Population	IXE80Q2W & IXE80Q4W vs. placebo at Weeks 16, 52 and all other postbaseline visits in Period 2
ANCOVA with mBOCF			ITT Population	IXE80Q2W & IXE80Q4W vs. placebo at Weeks 16 and 52 and all other postbaseline visits in Period 2	Health Outcomes/QOL analyses (Section 6.11).
	Proportion of patients with $\geq 3$ points	Logistic regression with NRI;	ITT population With Baseline Score $\geq 3$	IXE80Q2W & IXE80Q4W vs. placebo at Week 16, 52 and all other	Health Outcomes/QOL analyses

Measure	Variable	Analysis Method (Sections 6.1 and 6.3)	Population (Section 6.1.1)	Comparison/Time Point	Analysis Type
	improvement from baseline	Fisher’s exact test with NRI		postbaseline visits in Period 2	(Section 6.11).
	Proportion of patients reaching Good ASAS HI (defined as ASAS HI ≤5)	Logistic regression with NRI; Fisher’s exact test with NRI	ITT population With Baseline Score >5	IXE80Q2W & IXE80Q4W vs. placebo at Week 16, 52 and all other postbaseline visits in Period 2	Health Outcomes/ QOL analyses (Section 6.11).
Fatigue Severity Numeric Rating Scale	Fatigue Severity change from baseline	MMRM	ITT Population	IXE80Q2W & IXE80Q4W vs. placebo at Weeks 16 and 52 and all other postbaseline visits in Period 2	Health Outcomes/ QOL analyses (Section 6.11).
		ANCOVA with mBOCF	ITT Population	IXE80Q2W & IXE80Q4W vs. placebo at Weeks 16 and 52 and all other postbaseline visits in Period 2	Health Outcomes/ QOL analyses (Section 6.11).
Work Productivity and Activity Impairment Questionnaire—Spondyloarthritis	Change from baseline in: 
 
percentage of absenteeism
 
percentage of presenteeism
 
overall work impairment score
 
percentage of activity impairment
 
	ANCOVA with mBOCF	ITT Population	IXE80Q2W & IXE80Q4W vs. placebo at Week 16 and 52 in Period 2	Health Outcomes/ QOL analyses (Section 6.11).
JSEQ	JSEQ score change from baseline	MMRM	ITT Population	IXE80Q2W & IXE80Q4W vs. placebo at Weeks 16 and 52 and all other postbaseline visits in Period 2	Health Outcomes/ QOL analyses (Section 6.11).
		ANCOVA with mBOCF	ITT Population	IXE80Q2W & IXE80Q4W vs. placebo at Weeks 16 and 52 and all other postbaseline visits in Period 2	Health Outcomes/ QOL analyses (Section 6.11).
Quick Inventory of Depressive Symptomatology-self report 16 items	Change from baseline in the 9 QIDS-SR16 domains and Item 12 score	ANCOVA with mBOCF	ITT Population	IXE80Q2W & IXE80Q4W vs. placebo at Weeks 16 and 52 and all other postbaseline visits in Period 2	Health Outcomes/ QOL analyses (Section 6.11).
	Change from baseline		ITT Population with at		

Measure	Variable	Analysis Method (Sections 6.1 and 6.3)	Population (Section 6.1.1)	Comparison/Time Point	Analysis Type
	in QIDS-SR16 total score		least moderate depression at baseline (QIDS-SR16 total score $\geq 11$ )		
	Proportion of patients with at least a 50% decrease in QIDS-SR16 total score	Logistic regression with NRI; Fisher’s exact test with NRI	ITT Population for patients with at least moderate depression at baseline (QIDS-SR16 total score)	IXE80Q2W & IXE80Q4W vs. placebo at Weeks 16 and 52 and all other postbaseline visits in Period 2	

Abbreviations: ANCOVA = analysis of covariance; ASAS HI = Assessment of Spondyloarthritis International Society Health Index; IR = inadequate responder; ITT = intent-to-treat; IXE80Q2W = ixekizumab 80 mg every 2 weeks; IXE80Q4W = ixekizumab 80 mg every 4 weeks; JSEQ = Jenkins Sleep Evaluation Questionnaire; mBOCF = modified baseline observation carried forward; MCS = mental component summary; MMRM = mixed-effects model of repeated measures; NRI = nonresponder imputation; PCS = physical component summary; QIDS-SR16 = Quick Inventory of Depressive Symptomatology–Self-Report (16 Items); QOL = quality of life.

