#### Period 2 (Blinded Treatment Dosing Period):

Unless otherwise specified, the other secondary analyses during Period 2 will be based on the ITT population.

Treatment comparisons in the proportion of patients achieving a categorical response at a specified time point will be analyzed using the logistic regression model defined in Section 9.2.1. Missing data will be imputed using the NRI method described in Section 9.2.4.

For all continuous health outcomes variables that are collected at repeated visits, treatment group comparisons will be analyzed using the MMRM model defined in Section 9.2.1. No imputation methods are applied to MMRM analysis. Additional analysis will be conducted using ANCOVA model defined in Section 9.2.1. Missing data will be imputed by the mBOCF method as described in Section 9.2.4.

Additional analyses of health outcomes measures will be specified in the SAP.

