
Other secondary objectives are:
 
 
To compare both ixekizumab regimens (80 mg Q2W or 80 mg Q4W) to placebo during the 52-week period
 
	
 
Proportion of patients who achieve ASAS20, ASAS40, ASAS5/6, and partial remission by ASAS criteria
 
Change from baseline in the individual components of the ASAS criteria
 
Change from baseline in Bath Ankylosing Spondylitis Disease Activity Index (BASDAI)
 
Proportion of patients reaching BASDAI50
 

Objectives	Endpoints
	
 
• Change from baseline in ASDAS
 
• Proportion of patients who experience clinically-important improvement (change of ASDAS from baseline <math>\geq 1.1</math>), major improvement (change of ASDAS from baseline <math>\geq 2.0</math>), or inactive disease (ASDAS <math>< 1.3</math>), or ASDAS <math>< 2.1</math>
 
• Change from baseline in the measure of C-reactive protein (CRP)
 
• Change from baseline in Bath Ankylosing Spondylitis Functional Index (BASFI)
 
• Change from baseline in mobility                         
 
○ Bath Ankylosing Spondylitis Metrology Index (BASMI) (linear) and individual components
 
○ Chest expansion
 
○ Change from baseline in occiput to wall distance
 
 
 
• Change from baseline in MRI of the SIJ (SPARCC score)
 
• Change from baseline in SPARCC SIJ Structural Score (SSS)
 
• Change from baseline in Maastricht Ankylosing Spondylitis Enthesitis Score (MASES)
 
• Change from baseline in SPARCC Enthesitis Score
 
• The incidence and severity of peripheral arthritis by tender and swollen joint count scores of 46/44 joints
 
• Incidence rate of anterior uveitis or uveitis flares
 
• Change from baseline in the following health outcomes measures: Fatigue numeric rating scale (NRS) score, ASAS Health Index (HI) score, Jenkins Sleep Evaluation Questionnaire (JSEQ), Work Productivity Activity Impairment—Spondyloarthritis (WPAI-SpA) scores, SF-36 (both physical component [PCS] and mental component scores [MCS]), and Quick Inventory of Depressive Symptomatology–Self-Report (16 Items) (QIDS-SR16) score.
 
• Nonsteroidal anti-inflammatory drug (NSAID) intake (ASAS-NSAID score and % of patients taking NSAIDs)
 

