### **6.13.6. Quick Inventory of Depressive Symptomatology–Self Report 16 Items (QIDS-SR16)**

The QIDS-SR16 is a self-administered 16-item instrument intended to assess the existence and severity of symptoms of depression as listed in the American Psychiatric Association’s (APA’s) *Diagnostic and Statistical Manual of Mental Disorders, 4th Edition (DSM-IV)* (APA 1994). The QIDS-SR16 scale is used to assess the potential impact of treatment on new onset or changes in depression, thoughts of death, and/or suicidal ideation severity. A patient is asked to consider each statement as it relates to the way they have felt for the past 7 days. There is a 4-point scale for each item ranging from 0 to 3. The 16 items corresponding to 9 depression domains are summed to give a single score ranging from 0 to 27, with higher scores denoting greater symptom severity. Additional information and the QIDS-SR16 questions may be found at the University of Pittsburgh IDS/QIDS resource page (WWW).

The 9 domains assessed by the instrument are defined as:

- 1) **Sleep disturbance** (initial, middle, and late insomnia or hypersomnia): the highest score recorded for the 4 sleep items: #1 (falling asleep), #2 (sleep during the night), #3 (waking up too early) and #4 (sleeping too much). Domain is missing if all items are missing.
- 2) **Sad mood**: Item #5 (feeling sad). Domain is missing if the item is missing.
- 3) **Decrease/increase in appetite/weight**: the highest score recorded for the appetite/weight items: #6 (decreased appetite), #7 (increased appetite), #8 (decreased weight within the last 2 weeks), and #9 (increased weight within the last 2 weeks). Domain is missing if all items are missing or not applicable.
- 4) **Concentration**: Item #10 (concentration / decision making). Domain is missing if the item is missing.
- 5) **Self-criticism**: Item #11 (view of myself). Domain is missing if the item is missing.

- 6) **Suicidal ideation:** Item #12 (thoughts of death or suicide). Domain is missing if the item is missing.
- 7) **Interest:** Item #13 (general interest). Domain is missing if the item is missing.
- 8) **Energy/fatigue:** Item #14 (energy level). Domain is missing if the item is missing.
- 9) **Psychomotor agitation/retardation:** the highest score recorded for the 2 psychomotor items: #15 (feeling slowed down) and #16 (feeling restless). Domain is missing if all items are missing.

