The QIDS-SR16 total score is the sum of the above domain scores. The total score will be missing if any domain score is missing.

The QIDS-SR16 total scores are categorized as follows:

- None (no depression): 0 – 5
- Mild: 6 – 10
- Moderate: 11 – 15
- Severe: 16 – 20
- Very severe: 21 – 27.

The following summaries will be produced for QIDS-SR16 total score category by treatment groups for the Safety Population during the Period 2:

- The number and percentage of patients falling into each QIDS-SR16 total score category at each scheduled visit.
- Shift from maximum baseline to each postbaseline visit in QIDS-SR16 total score category.
- The number and percentage of patients falling into the following categories based upon the maximum postbaseline QIDS-SR16 total score:
  - Improved; maximum postbaseline category < maximum baseline category.
  - Worsened; maximum postbaseline category > maximum baseline category.
  - Same; maximum postbaseline category = maximum baseline category.

In addition, the number and percentage of patients falling into the following groups based upon the maximum postbaseline QIDS-SR16 item 12 (Thoughts of Death or Suicide) score will be summarized by treatment groups for Safety Population during Period 2:

- Improved; maximum postbaseline QIDS-SR16 item 12 score < maximum baseline item 12 score.
- Worsened; maximum postbaseline QIDS-SR16 item 12 score > maximum baseline item 12 score.
- Same; maximum postbaseline QIDS-SR16 item 12 score = maximum baseline item 12 score.

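### Change in QIDS-SR16 total score is listed for all patients, but SAP Table RHBX.6.7 compares it with placebo only in those scoring 11 or more at baseline

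*SAP*

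**What the plan says.** **The endpoint.** Protocol Section 3 (Table RHBX.1) and SAP Section 4 both include, among the other secondary health outcomes compared with placebo over 52 weeks, change from baseline in the "Quick Inventory of Depressive Symptomatology–Self-Report (16 Items) (QIDS-SR16) score". Neither attaches a baseline threshold.

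**The default population.** Protocol 9.7.1 states: "Unless otherwise specified, the other secondary analyses during Period 2 will be based on the ITT population". SAP 6.11 states: "The analyses of health outcomes and QOL measures for Period 2 will be based on the ITT Population".

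**The detailed plan.** SAP Table RHBX.6.7 has three QIDS-SR16 entries:

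- "Change from baseline in the 9 QIDS-SR16 domains and Item 12 score": ANCOVA with mBOCF, full ITT Population, each regimen against placebo at Weeks 16 and 52 and the other postbaseline visits.
- Change in total score: only ITT patients with at "least moderate depression at baseline (QIDS-SR16 total score" of 11 or more).
- A decrease of at least 50% in total score: logistic regression and Fisher's exact test with NRI, also in patients at least moderately depressed at baseline. The cut-off is not legible in this row, which may be a conversion loss and is not held against the plan.

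**The safety section.** SAP 6.13.6 says the scale is used to "assess the potential impact of treatment on new onset or changes in depression, thoughts of death, and/or suicidal ideation severity". It bands the total as none (0–5), mild (6–10), moderate (11–15), severe (16–20) and very severe (21–27). By treatment group in the Safety Population, it reports the category at each visit, the shift from maximum baseline category to each visit, and improved/worsened/same for both the total score category and Item 12.

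**The concern.** An endpoint written for every randomised patient should have at least one comparison in every randomised patient. Here the only between-group analysis of change in the total is confined to a severity subset. The narrowing appears in a table cell, without a rationale, and against the general statement in 6.11. Anyone reading Section 4 would expect an ITT result, and the planned output will not contain one.

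The subset also answers a narrower question. It shows whether depressive symptoms change in patients who start at least moderately depressed. It does not show how the total moves on ixekizumab against placebo in the trial population, most of whom may start in the none or mild bands. At stake is the completeness and precision of one other secondary endpoint that lies outside the multiplicity scheme.

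**Working it through.** The documents give no sample size, SD, effect size or baseline distribution for QIDS-SR16, so there is no stated figure to reproduce. The check is a comparison of sections, followed by an illustration of size.

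**Step 1: which QIDS-SR16 analyses cover all patients?**

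| Quantity | Population | Between-group analysis | Place in SAP |
|---|---|---|---|
| Nine domains, Item 12: change | Full ITT | ANCOVA with mBOCF | Table RHBX.6.7 |
| Total score: change | ITT, baseline ≥11 | ANCOVA with mBOCF | Table RHBX.6.7 |
| Total score: ≥50% decrease | ITT, at least moderate at baseline | Logistic regression, Fisher, NRI | Table RHBX.6.7 |
| Total score category, shifts, worsening | Safety, all severities | By group; general Fisher rule for categorical safety data (6.1.2.1) | 6.13.6 |
| Item 12 worsening | Safety, all severities | As above | 6.13.6 |
| Depression and self-injury TEAEs | Safety | Fisher | Table RHBX.6.8 |

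The combination of total score, change and all patients does not occur.

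**Step 2: can it be recovered from the other rows?** SAP 6.13.6 states: "The QIDS-SR16 total score is the sum of the above domain scores". Nine domains scored 0 to 3 give the maximum of 9 × 3 = 27. But the variance of a sum is the sum of the variances plus twice the sum of the covariances. Nine domains have 9 × 8 / 2 = 36 pairs, and separate domain ANCOVAs report none of these covariances. Each domain model also adjusts for its own baseline. Nine domain results therefore do not give a confidence interval for the total.

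The category summaries do not replace it either. A move from 0 to 5, or from 6 to 10, stays within one band and is counted as no change.

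**Step 3: illustration of size.** Inputs: 100 per arm (SAP 5.2); share f of patients scoring ≥11, assumed to be 10% to 30% and equal across arms; same SD in the subset as in the whole; two-sided 0.05; normal approximation.

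- Subset size per arm: n = 100f
- Standard error relative to full ITT: 1/√f
- Difference detectable with 80% power, in SD units: (1.96 + 0.84) × √(2/n)
- Power for a difference of 0.40 SD: Φ(0.40 × √(n/2) − 1.96)

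| f | n per arm | SE ratio | Detectable difference (SD) | Power at 0.40 SD |
|---|---|---|---|---|
| 100% (full ITT) | 100 | 1.00 | 0.40 | 81% |
| 30% | 30 | 1/√0.3 = 1.83 | 0.72 | 34% |
| 20% | 20 | 1/√0.2 = 2.24 | 0.89 | 24% |
| 10% | 10 | 1/√0.1 = 3.16 | 1.25 | 14% |

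Under this assumption, 70% to 90% of patients do not enter the total-score comparison.

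**The case against.** **The restriction is within the plan's rules.** Protocol 9.7.1 and SAP 6.1.1 allow exceptions to ITT, and 6.11 sends the reader to Table RHBX.6.7 for the detailed population. This stands: the subset is not a violation. It does not supply a reason, and it leaves the listed endpoint without an analysis in its listed population.

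**Baseline restrictions are common in this SAP.** Enthesitis and joint-count changes require a baseline score above zero, and ASDAS <2.1 requires a baseline of 2.1 or more. This partly stands. The enthesitis and joint rules remove patients without the manifestation, whereas a score of 6–10 is mild depression by the SAP's own bands, and those patients can move either way. The closer comparison is ASAS HI in the same table: mean change is in full ITT, and only its threshold endpoints carry a baseline cut.

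**A smaller standard error is not the whole story.** The two analyses estimate different things, and low scorers have little room to improve. Full ITT may therefore be no more powerful for improvement. This stands, and the table above is only an illustration of precision at equal SD.

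**Stronger readings that a reader might infer.** One is that worsening mood is missed, or survives only in unadjusted category counts. The documents do not support that. A patient who moves from none or mild to moderate is counted as worsened in 6.13.6 whatever the baseline. Item 12 worsening is counted in the same way, and depression adverse events are compared between groups. The nine domains and Item 12 are compared in all ITT patients with adjustment for baseline, region and screening MRI/CRP status. Another is that the subset can only show improvement. That is also too strong, since a patient at 11 can still worsen and randomised placebo patients regress to the mean as well.

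**Conclusion.** The point holds as an unexplained narrowing of one other secondary endpoint. Change in QIDS-SR16 total score is listed for all patients and will be compared with placebo only in those at 11 or above. The resulting gap is an all-patient estimate of change in the total with its confidence interval; movement within a severity band is also not visible in the category summaries. It is not a gap in safety monitoring.

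The loss of precision depends on a share the documents do not give. At 10% to 30%, the standard error is about 3.2 to 1.8 times that of full ITT, assuming equal SD and 100 per arm. A larger share would shrink this: at 50% the ratio is 1/√0.5 = 1.41. The endpoint carries no power claim and no multiplicity control, and no primary, major secondary or safety conclusion rests on it. The point is minor, but worth correcting because the correction is almost free.

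**What to change.** In SAP Table RHBX.6.7, add a row for change from baseline in QIDS-SR16 total score in the full ITT Population: ANCOVA with mBOCF, each regimen against placebo, at Weeks 16 and 52 and the other scheduled postbaseline visit (Week 36 in the protocol's Schedule of Activities). Keep the baseline ≥11 analysis and the 50% decrease endpoint, labelled as supportive. If the sponsor prefers the subset as the only analysis, Section 4 and 6.11 should say so and give the reason.

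The cost is one table row and one more run of a program already planned for the domains. No new data are needed.
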